7.4.2 Data Collected During the Treatment Visits

- CGM glucose every 5 minutes from the Dexcom G4 Platinum CGM
- All BG measurements taken
- Insulin total dose by the BP and the patient's own insulin pump
- Glucagon total dose
- Timing and content of the meal eaten and carbohydrate amount
- Timing of meal announcement and size of meal announced
- Timing and glucose values at calibrations
- Timing and amount of carbohydrates taken for hypoglycemia
- Data from a questionnaire about attitudes and expectations regarding the BP before and after each treatment arm (see [Appendix C](#))
- Time patients were not under BP control for any reason
- List of technical faults associated with the BP including cause and resolution
- ZP4207/glucagon sampling will be collected at least hourly. If BG is <150 mg/dL, more frequent samples for plasma ZP4207/glucagon may be drawn at the discretion of the Investigator.
- Plasma glucose sampling will be collected at least hourly in parallel with ZP4207/glucagon exposure sampling. If BG is <150 mg/dL, then sampling will be every 30 minutes. If BG is <100 mg/dL, then sampling will be every 20 minutes. If BG is <80 mg/dL, then sampling will be every 10 minutes.
- Nausea and infusion site pain on a VAS at visit start (after insertion and before any drug administration), hourly, and at visit end
- Infusion site reaction according to the Draize scale at visit start (after insertion and before any drug administration), hourly, and at visit end
- Patient reports of symptoms, any other complaints, and AEs
- Vital signs including body temperature and blood pressure (at visit start and visit end) and weight
- Concomitant medications

Clinical Trial Protocol
ZP4207-16051

Version number: 3.0
Amendment 2.0
Date: 03 August 2016

- Chemistry and hematology samples (see [Appendix B](#)) at visit start and visit end
- ADA (Visit 3 only)
- 12-lead ECG at visit start and visit end
- Urine HCG pregnancy test for women of childbearing potential

7.4.3 Response to Hypoglycemia

- Patients are encouraged to check their BG for any symptoms of hypoglycemia.
- Patients will be permitted to take 15 grams of carbohydrates for any BG value <60 mg/dL. Trial staff will ensure proper functioning of the BP, infusion set, and insulin pump, and will encourage the patient to wait for the BP to treat the low blood sugar for as long as they feel comfortable.
- Patients will be required to take 15 grams of carbohydrates for any BG value <50 mg/dL. After treatment of hypoglycemia, a follow-up measurement will be taken 15 minutes later. Repeated measurements will be taken every 15 minutes until the BG is >60 mg/dL. Treatment will be repeated if subsequent BG values are still <50 mg/dL. All carbohydrate treatments for hypoglycemia will be documented by trial staff (amount and time).
- Trial staff will check the infusion site, BP, and insulin pump for normal operation any time hypoglycemia occurs. If there is any suspicion of infusion set malfunction, the site should be replaced. Trial staff will check the BP for any malfunction and correct any problems that are found.
- If no correctable fault is found, but there is doubt regarding the correct function of the BP system, an entirely new backup BP system may be started.
- If a patient experiences a seizure or unconsciousness associated with hypoglycemia, his or her participation in the trial will be discontinued.

7.4.4 Response to Hyperglycemia

- Trial staff will check the infusion site, BP, and insulin pump for normal operation any time BG is >300 mg/dL. If there is any suspicion of infusion set malfunction, the site should be replaced. Trial staff will check the BP for any malfunction and correct any problems that are found. If the BG remains >300 mg/dL for 2 hours despite troubleshooting, blood ketones will be measured. If the blood ketone result is >1.5 mmol/L, the visit will be stopped and rescheduled. The patient will be provided with insulin and a syringe to give an injection based on their correction factor.
- If a patient experiences diabetic ketoacidosis, his or her participation in the trial will be discontinued.
- If no correctable fault is found, but there is doubt regarding the correct function of the BP system, the treatment visit may be stopped and the visit rescheduled.

7.4.5 Response to Nausea/Vomiting

If significant nausea (e.g., that prevents the patient from eating normally) or any vomiting occurs, trial staff will notify the Investigator. Trial staff will assist the patient in troubleshooting, such as checking BG and the calibration of the CGM (excessive glucagon dosing may occur if the CGM is reading lower than the true BG). If a patient experiences persistent nausea and vomiting thought to be related to glucagon dosing, his or her participation in the trial will be discontinued.

Clinical Trial Protocol
ZP4207-16051

Version number: 3.0
Amendment 2.0
Date: 03 August 2016

7.4.6 Response to Other Medical Needs

If patients experience urgent or emergent medical concerns outside the scope of diabetes care and their primary care physicians, they will be taken to the MGH walk-in clinic or emergency room, or if necessary call 911.

7.4.7 Monitoring of Bionic Pancreas Performance

Bionic pancreas inventors and developers [REDACTED], [REDACTED], and/or an engineer trained by them will be readily available by phone for consultation for the trial staff at all times during the course of the trial.

7.4.8 Supervision by Trial Staff

A trial MD will be on call at all times during the course of the trial. An RN or MD will be with the trial patients in the Diabetes Research Center at all times.

7.5 Phone Call (Visit 5)

A phone call will be conducted 7 days \pm 3 days following the last day of dosing (Visit 4) to review AEs and concomitant medications.

7.6 Follow-up Visit (Visit 6)

Patients will return for a Follow-up Visit 25 days \pm 4 days following the last day of dosing (Visit 4), for chemistry, hematology, and ADA sampling, and a review of AEs and concomitant medications.

8 ENDPOINTS

8.1 Primary Endpoint

The primary endpoint is the safety and tolerability of ZP4207 and the iLet as assessed by:

- Number and type of AEs
- Clinical laboratory measurements
- Vital signs
- 12-lead ECG
- Local tolerability and infusion site reactions as measured with the Draize scale
- Immunogenicity as measured by ADA
- Pain as measured on a 10 cm VAS
- Nausea as measured on a 10 cm VAS

8.2 Secondary Endpoints

The secondary endpoints for the iLet and ZP4207 include measurements of BP function as well as glycemic and non-glycemic measurements.

8.2.1 Bionic Pancreas Function

This endpoint data will be generated from the BP data during each treatment visit:

- Average percent insulin dose amounts calculated by the BP control algorithm that are successfully delivered by the pump
- Average percent glucagon/ZP4207 dose amounts calculated by the BP control algorithm that are successfully delivered by the pump

Clinical Trial Protocol
ZP4207-16051

Version number: 3.0
Amendment 2.0
Date: 03 August 2016

- Average percent dose amounts successfully issued to the pump by the BP control algorithm that are successfully delivered by the pump (calculated doses are not issued unless the pump is accessible and its delivery channel is available)
 - Average percent insulin dose amounts successfully issued to the pump by the BP control algorithm that are successfully delivered by the pump
 - Average percent glucagon/ZP4207 dose amounts successfully issued to the pump by the BP control algorithm that are successfully delivered by the pump
- Average percent dose amounts calculated by the BP algorithm that are successfully issued to the pump by the BP (calculated doses are not issued unless the pump is accessible and its delivery channel is available)
 - Average percent insulin dose amounts calculated by the BP control algorithm that are successfully issued by the BP
 - Average percent glucagon/ZP4207 dose amounts calculated by the BP control algorithm that are successfully issued by the BP
- Average percent of 5-minute steps during which the BP is functioning nominally in all respects based on real-time CGM data (new CGM glucose reading captured, dose calculated, and dose issued to pumps)
- Average percent of 5-minute steps during which the BP is functioning nominally with or without a new CGM glucose reading captured (dose calculated and dose issued to pumps). If a CGM signal is not available, the dose calculated may be based on weight or historical basal rates.
- CGM reliability index, calculated as percent of possible values actually recorded by CGM
- CGM Mean Absolute Relative Difference versus time-stamped BG values from meter download
- List of technical faults associated with the BP including cause and resolution

8.2.2 *Glycemic*

All of following metrics will be generated from the Dexcom G4 Platinum CGM data during each treatment visit.

- Fraction of time spent within each of the following glucose ranges:
 - <50 mg/dL
 - <60 mg/dL
 - <70 mg/dL
 - 70-120 mg/dL
 - 70-140 mg/dL
 - 70-180 mg/dL
 - >180 mg/dL
 - >250 mg/dL
 - >300 mg/dL
- Number of severe hypoglycemic events (patients unable to self-treat, requiring the assistance of another person)
- Number of episodes of symptomatic hypoglycemia
- Number of carbohydrate interventions for hypoglycemia
- Total grams of carbohydrates taken for hypoglycemia
- Mean CGM glucose

Clinical Trial Protocol
ZP4207-16051

Version number: 3.0
Amendment 2.0
Date: 03 August 2016

8.2.3 **Non-glycemic**

- Glucagon/ZP4207 total delivery per kg of body mass
- Insulin total delivery per kg of body mass
- Number of unscheduled infusion set replacements
- Number of unscheduled CGM sensor changes

9 **LABORATORY ASSESSMENTS**

Descriptions of sample handling and sample processing, storage, and shipment at the site will be included in the laboratory manual.

The responsible laboratories are listed in the [address list](#).

9.1 **Safety Laboratory Assessments**

Chemistry and hematology samples will be collected at specified time points. See [Appendix A](#) for the schedule of procedures and [Appendix B](#) for a list of clinical laboratory analytes.

9.2 **Pharmacodynamic Assessments (Plasma Glucose)**

At Visit 3 and Visit 4, plasma glucose samples will be taken from the IV at least hourly in parallel with ZP4207/glucagon exposure sampling and measured using the YSI 2300 STAT Plus. If the YSI 2300 STAT Plus and/or IV fails, the Nova StatStrip Xpress will be used for glucose measurements. If BG is <150 mg/dL, then sampling will be every 30 minutes. If BG is <100 mg/dL, then sampling will be every 20 minutes. If BG is <80 mg/dL, then sampling will be every 10 minutes. The actual time of sampling will be recorded in the eCRF.

9.3 **Exposure Assessments (ZP4207 and Glucagon)**

At Visit 3 and Visit 4, ZP4207/glucagon exposure sampling will be collected at least hourly. If BG is <150 mg/dL, more frequent samples for plasma ZP4207/glucagon may be drawn at the discretion of the Investigator. The actual time of sampling will be recorded in the eCRF.

Bioanalytical Reports will be prepared.

9.4 **Anti-drug Antibody Assessments**

Blood samples (including back-up samples) for serum anti-ZP4207 and anti-glucagon antibodies will be taken at Visit 3 and the Follow-up Visit 6.

A Bioanalytical Report will be prepared.

10 **SAFETY REPORTING**

10.1 **Adverse Events**

An AE is any untoward medical occurrence in a trial patient administered an IMP and which does not necessarily have a causal relationship with the treatment. An AE can therefore be any unfavorable and unintended sign (e.g., an abnormal laboratory finding), symptom, or disease temporally associated with the use of an IMP, whether or not considered related to the IMP. Patients should be instructed to report any AE they experience to the Investigator.

Clinical Trial Protocol
ZP4207-16051

Version number: 3.0
Amendment 2.0
Date: 03 August 2016

Note: This includes events from the first trial-related activity from Visit 3.

AEs for ZP4207 include:

- A clinically significant worsening of a concomitant illness
- A clinical laboratory abnormality which is clinically significant, i.e., any abnormality that suggests a disease and/or organ toxicity and is of a severity that requires active management. Active management includes active treatment or further investigations, for example, change of medicine dose or more frequent follow-up due to the abnormality.
- Hypoglycemic episodes
- Injection site reactions

The following should **not** be recorded as AEs, if recorded prior to randomization (on the Screening Form or the eCRF):

- Pre-planned procedure, unless the condition for which the procedure was planned has worsened from the first trial-related activity from Visit 3.
- Pre-existing conditions found as a result of screening procedures (pre-existing conditions should be reported as medical history or concomitant illness).

For known (listed) AEs for Glucagon and Humalog, please refer to SPC for [Glucagon](#) and [Humalog](#).

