7.4.1 Visit Procedures

- Patients will be asked to arrive at the visit at least 1 hour in advance of the start of the BP having fasted since 12:00 AM the night before (treatment with simple carbohydrate of up to 30 g for a low is allowed). If the patient is not fasted, the visit will be rescheduled within the visit window. If BG is >250 mg/dL, the visit will be rescheduled within the visit window. If BG is <50 mg/dL, treatment with simple carbohydrate is allowed. If the patient experiences persistent hypoglycemia, the visit will be rescheduled within the visit window. If the visit needs to be rescheduled due to hypoglycemia or hyperglycemia, trial staff will assist the patient with insulin or medication adjustments to address glycemic control. The patient will be instructed to contact trial staff later in the day if his or her BG remains uncontrolled.
- Upon arrival to the visit, the patient's weight and vital signs including body temperature and blood pressure will be documented.
- Patient reports of symptoms, any other complaints, and AEs will be reviewed.
- Concomitant medications will be recorded.
- Chemistry and hematology samples will be collected at visit start (see [Appendix B](#)).
- ADA samples will be collected before the start of dosing (Visit 3 only).
- A 12-lead ECG will be performed.
- A urine HCG pregnancy test will be performed in female patients of childbearing potential. If the test is positive, the patient will be informed of the result and the visit will be ended.
- Patients will complete a baseline survey about their attitudes and experience with their usual diabetes care.
- An intravenous (IV) catheter will be placed for blood sampling.

Clinical Trial Protocol
ZP4207-16051

Version number: 3.0
Amendment 2.0
Date: 03 August 2016

- Trial staff will assist the patient to calibrate their CGM, review the trial procedures again and assist with the setup of the BP system, including inserting and priming infusion sets.
- The control algorithm will be initialized only with the patient's weight. Diagnostics will be performed to ensure that the CGM device is appropriately calibrated and that all of the components of the BP systems are in working order.
- The basal rate of the patient's own insulin infusion pump will be changed to be 2-fold higher than weighted mean of the basal rate during the trial period. This is intended to increase the usage of glucagon during the treatment visit.

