- Patients will exercise on a stationary bike with a heart rate from 120-140 beats per minute for a total of 4,000 heart beats (approximately 30 minutes). Patients will rate their exercise intensity using the Borg scale every 5 minutes, with the target intensity level between 12 and 14. Heart rate will be measured every 5 minutes.
- BG measurements will be obtained off of the IV line every 10 minutes. If BG is <80 mg/dL, BG measurements will be obtained off of the IV line every 5 minutes.
 - Carbohydrates will be given for any BG <50 mg/dL according to the following protocol: Dextrose (g) = BSA (m²)/[1.7 m² (women) or 1.9 m² (men)] *15 g.
 - Repeat treatments will be given at 15-minute intervals as long as BG remains <50 mg/dL.
- If there is an interruption in the Dexcom CGM output, trial staff will assist the patient in recovering CGM data streaming. If this requires replacement of the CGM sensor, BGs will be checked every 10 minutes (every 5 minutes if BG is <80 mg/dL) using blood from the IV until the CGM is able to be calibrated again. These BGs will be entered into the BP, which will treat them as CGM values and dose insulin and/or glucagon appropriately.
- If there is a complete failure of the BP operation, patients will take over their own BG control using their personal insulin pump until the BP can be brought back online. If BP control cannot be promptly resumed (e.g., within 30 minutes), the patient may be asked to repeat that trial day once.
- Patients may choose to withdraw from the trial at any time. If they withdraw from the trial, they should alert a provider immediately.
- Just prior to the end of the study visit, vital signs including body temperature and blood pressure will be obtained and a 12-lead ECG will be performed.
- After approximately Hour 8, but not earlier than at least 60 minutes after end of exercise, the BP will be stopped and the patient will continue with their personal insulin pump.

Clinical Trial Protocol
ZP4207-16051

Version number: 3.0
Amendment 2.0
Date: 03 August 2016

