11.2.2 Analysis of Efficacy

The analysis of BP function endpoints and glycemic endpoints will be on an intention-to-treat basis. In cases where a treatment arm was not completed (and that arm was not repeated according to protocol criteria), available data from that arm will be used in the data analysis.

The Shapiro-Wilk test will be used to determine the normality of the residuals for each comparison. Summary tables that display descriptive statistics, including percentages, means or medians, and standard deviation and/or ranges, as appropriate, will be provided.

Clinical Trial Protocol
ZP4207-16051

Version number: 3.0
Amendment 2.0
Date: 03 August 2016

A paired t-test or the Wilcoxon signed rank test for comparison of means with normally or non-normally distributed residuals, respectively, will be used. In a secondary analysis, any period effect and any interaction between treatment and period will be looked for, although no such interaction is predicted for the efficacy outcome. Further details will be included in the SAP.

The number of patients and proportions of severe hypoglycemic events, symptomatic hypoglycemia, and carbohydrate interventions due to hypoglycemia with the event counts will be summarized descriptively, and the proportions will be analyzed by a Fisher's exact test if data allow.

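### Hypoglycemia, carbohydrate and delivery endpoints are unadjusted per-visit counts or totals, and unrepeated short visits are analyzed as they stand, which modestly favors the less tolerated product

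*Protocol*

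**What the plan says.** Protocol 8.2.2 opens with "All of following metrics will be generated from the Dexcom G4 Platinum CGM data during each treatment visit". The glucose-range endpoints that follow are fractions of time. The others are not: severe hypoglycemic events, "Number of episodes of symptomatic hypoglycemia", carbohydrate interventions and "Total grams of carbohydrates taken for hypoglycemia" are plain counts or sums. Section 8.2.3 adds "Glucagon/ZP4207 total delivery per kg of body mass" and the matching insulin total, scaled by body mass but not by time.

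Section 11.2.2 covers an arm that was not completed and not repeated under the protocol's own criteria: "available data from that arm will be used in the data analysis". It gives no adjustment for time observed. Means are compared by paired t-test or Wilcoxon signed rank test. The three hypoglycemia and intervention counts are described, and the proportions go to Fisher's exact test if the data permit.

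Stops are treated differently by cause:

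- **Device failure (7.4.1):** the day may be repeated once.
- **Ketones above the threshold (7.4.4):** the visit is stopped and rescheduled.
- **Continuing or recurring site reactions (7.4.1):** the patient is discontinued.
- **Persistent nausea and vomiting attributed to glucagon (4.4, 7.4.5):** the patient is discontinued.

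**The concern.** A count or total grows with time observed. If one product's visits are shorter, its hypoglycemia and carbohydrate figures fall whatever its effect on glucose.

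The repeat and reschedule rules remove many of the stops that have nothing to do with tolerability. They leave in the data the stops that end participation, among them the two tied to nausea and infusion-site tolerability. A hypoglycemic seizure, ketoacidosis or voluntary withdrawal would also leave a short visit, so not every short visit is an intolerance stop. The mixture still leans that way, and the error always lowers the count.

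The missing hours also differ from the observed ones. Exercise starts between Hours 6 and 7, so any visit stopped earlier omits it. The fraction-of-time endpoints have a denominator, but for such a visit they describe only the earlier hours and are set against a full day on the other product. Time below 60 mg/dL, named in the secondary objective (2.2), is one of these.

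**Working it through.** The protocol states no sample size, power or event-rate calculation (11.2.4), so there is no figure to reproduce. The check is arithmetic on expected counts.

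**Inputs from the protocol.** The nominal visit is 8 hours (7.4.1) and exercise starts at Hour 6 to 7 (7.4.1). The calculation uses 10 patients; the protocol expects 10 to 12 randomized (11.2.4).

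**Assumptions not in the protocol.** The true rate is equal on both products, at 1 event per full visit. One to three of 10 visits stop at Hour 2, 4 or 6. The ratios of means below do not depend on the rate chosen.

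**Formula.** With k of 10 visits stopped at hour t, the expected mean count is [(10 − k) + k × F(t)] / 10, where F(t) is the share of events expected by hour t. For a constant rate F(t) = t/8. For a late-loaded pattern with half of events after Hour 6, F(t) = 0.5 × t/6 for t up to 6.

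**One visit stopped at Hour 4.** Constant rate: (9 + 0.5)/10 = 0.95. Late-loaded: (9 + 0.333)/10 = 0.933. The true value is 1.00.

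Mean count, constant rate / late-loaded:

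| Stop hour | 1 visit | 2 visits | 3 visits |
|---|---|---|---|
| 2 | 0.925 / 0.917 | 0.850 / 0.833 | 0.775 / 0.750 |
| 4 | 0.950 / 0.933 | 0.900 / 0.867 | 0.850 / 0.800 |
| 6 | 0.975 / 0.950 | 0.950 / 0.900 | 0.925 / 0.850 |

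The inverse of each cell is the true rate ratio that would look like equality: from 1/0.975 = 1.03 to 1/0.750 = 1.33.

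**Proportion with any event (the Fisher comparison).** For a full visit it is 1 − e^(−1) = 0.632. With one of 10 stopped at Hour 4 at a constant rate, it is 0.9 × 0.632 + 0.1 × (1 − e^(−0.5)) = 0.608.

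**Which analyses are exposed.** A patient discontinued at Visit 3 has no Visit 4 and contributes no pair, so paired tests are biased only by stops at Visit 4. Descriptive counts and the Fisher comparison are affected by stops at either visit.

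**Does a rate repair it?** At a constant rate, yes: one stop at Hour 4 gives 9.5 events in 9 × 8 + 4 = 76 hours, and 9.5/76 × 8 = 1.0 per 8 hours. With late-loaded events, only in part: 9.333/76 × 8 = 0.98 pooled. For the affected patient it is 0.333/4 × 8 = 0.67 against a true 1.0. Hence the need for a matched window as well.

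**Should the window end at Hour 8?** Exercise of 4,000 beats at 120 to 140 per minute lasts 28.6 to 33.3 minutes. A start at Hour 7 can end at Hour 7.56. The protocol says "After approximately Hour 8, but not earlier than at least 60 minutes after end of exercise, the BP will be stopped", which puts that stop at Hour 8.56. A cap at Hour 8 would keep only (8 − 7.56) × 60, or about 27 of those 60 minutes.

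**The case against.** The strongest reply is that the affected endpoints are secondary, in a feasibility trial, and that intolerance is itself the primary endpoint (8.1: adverse events, nausea, pain, Draize scale). A product stopped for nausea will show it there. This stands. A reader might infer that the comparison is turned upside down; the protocol does not support that, only a modest tilt in secondary results.

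Other limits also stand:

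- A reader might count ketone stops as partial data. Section 7.4.4 reschedules them, and 11.2.2 covers only arms that were not repeated.
- A reader might suppose that every short visit enters a paired test. Visit 3 discontinuations do not.
- The protocol has patients arrive early ("Patients will be asked to arrive at the visit at least 1 hour in advance of the start of the BP"), and a reader might infer that pre-start readings and arrival carbohydrate contaminate the endpoints. The protocol does not say that they are included. The arrival rules are the same at both visits and the order is randomized, so this would add noise rather than bias. The same holds for completed visits ending anywhere from about Hour 8.0 to 8.6.
- Less drug delivered in a shorter visit is a true record of exposure, and the intention-to-treat sentence in 11.2.2 names BP function and glycemic endpoints, not the non-glycemic ones. The delivery totals share the scale problem, but the bias claim rests on hypoglycemia and carbohydrate.
- More than one withdrawal for the 4.4 reasons halts the trial pending a DSMB vote, so two nausea stops could arise only by reaching that halt. Site-reaction stops are not on that list.

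Finally, 11.2.2 leaves further detail to the SAP, which could add an exposure adjustment. That does not dispose of the point, because the protocol itself fixes both the endpoint scale and the use of partial data.

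**Conclusion.** The point holds in a limited form. Applied as written, the endpoint definitions and the partial-data rule lower hypoglycemia and carbohydrate figures for whichever product has more unrepeated short visits, and the repeat rules make that more likely to be the less tolerated one.

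The size is about 5% of the arm mean per visit stopped at Hour 4 in 10 patients at a constant rate, or about 7% if half of events follow Hour 6. The stop hour, the number of stops and the late-loaded pattern are assumptions. The protocol gives no stop rate, and with no unrepeated early stops there is no such bias. The point is worth correcting before data are seen because the trial is meant to show that comparable glycemic control is feasible (1.1).

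**What to change.** In 8.2.2 and 8.2.3, set the observation window from Hour 0 (BP start) to the actual BP stop, with no cap at Hour 8. Express counts, grams and delivered doses per hour under BP control, and report observed hours per arm.

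For a patient whose Visit 4 is cut short at hour t, add a sensitivity comparison over the same Hour 0-to-t window in both visits, for the count and the fraction-of-time endpoints.

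The cost is endpoint wording and one extra table. Procedure times (7.4), Hour 0 (7.4.1) and time off BP control (7.4.2) are already recorded, and no treatment, rescue or stopping rule changes. The one drawback is that the matched comparison leaves out the other visit's later hours for that patient. Those hours remain in the main analysis.
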